3. *Provide the scientific or scholarly background for, rationale for, and significance of the research based on the existing literature and how it will add to existing knowledge:* Cardiac cachexia, a complex wasting condition characterized by skeletal muscle loss (sarcopenia), anorexia, inflammation and abnormal biochemistry, is associated with increased morbidity and mortality for patients with systolic heart failure (HF). There are currently no nutritional or pharmacological interventions demonstrated to reverse the cardiac cachexia syndrome. We have forged a collaboration between HF cardiology and nutrition specialists at Tufts Medical Center to develop methods for body composition assessment in end-stage systolic HF patients receiving left ventricular assist devices (LVADs). Our preliminary data demonstrates that as many as half of end-stage systolic HF patients have significant sarcopenia at the time of LVAD implantation and that skeletal muscle mass improves in the first six months of LVAD support. We have also identified mechanistic contributions with patients who are sarcopenic at the time of LVAD implantation having higher resting energy expenditure and greater levels of inflammation, as compared to patients without sarcopenia. Serum metabolomics identified lower levels of the branched-chain amino acids (BCAAs) valine, leucine, and isoleucine in sarcopenic patients, with restoration of BCAA levels at three months after LVAD implantation.

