Having demonstrated that sarcopenia can be reversed with LVAD implantation for patients with end-stage HF, the next step is to determine how early sarcopenia onset occurs within the natural history of systolic HF and develop an effective intervention for patients with less advanced HF. It is likely that an optimal intervention to reverse skeletal muscle mass in patients with HF will require elements of muscle substrate provision, anti-inflammatory activity and a pro-anabolic stimulus, and will probably be implemented early in the muscle loss trajectory. DXA is not an ideal technique for measuring changes in skeletal muscle mass during a sarcopenia reversal clinical trial because it is not widely available across medical centers. We also recognize that to bring sarcopenia diagnosis and treatment to the wider population of patients with systolic HF we must develop a method for inexpensive, bedside quantification of skeletal muscle mass to replace the current use of dual-energy X-ray absorptiometry (DXA). Therefore we seek to determine the utility of skeletal muscle ultrasound (US) as a novel method for sarcopenia diagnosis in patients with heart failure, given its

promising data in elderly patients with sarcopenia. Takai et al. (2014) compared skeletal muscle mass measurements by ultrasound to those acquired by DXA scan in 77 elderly subjects. They generated a regression equation using several anatomical ultrasound muscle thickness measurements to predict muscle mass measured by DXA. Ultrasound measurements of skeletal muscle have been evaluated in 2 systematic reviews (Nijholt 2017, English 2012) and have shown good performance for the prediction of lean mass. We hypothesize that DXA measurements of appendicular lean mass (ALM) will show adequate agreement with skeletal muscle US in systolic HF patients for deployment in our future HF body composition studies.

4. *Describe the relevance and usefulness of the objectives:* Measuring muscle mass will allow us to identify patients with HF who are experiencing muscle wasting. Comparing DXA scan and ultrasound measurements will demonstrate the validity of ultrasound method as a primary method for measuring muscle mass. The use of muscle ultrasound as a portable and non-ionizing screening method furthers our efforts to pursue effective therapies for cardiac cachexia.

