1. Describe the purpose, specific aims, or objectives of the study (i.e. the reason for performing the study in terms of the scientific question to be answered): The primary objective of this study is to validate the use of ultrasound muscle thickness measurements to determine muscle mass. The secondary aim of this study is to use accurate muscle mass measurements to categorize patients as cachectic or sarcopenic.

Note: Specify which are the primary or secondary aims or objectives of this study as applicable. The primary objective is the main question. Secondary objectives are goals that will provide further information for the study.

D. Enrollment and Withdrawal

D.1 Inclusion Criteria

1. Describe the criteria that define who will be **included** in the study as a numbered list:
2. Inclusion criteria:
 1. Cohort A: Healthy volunteers (who may be employees)
 - 18+ years
 - No history of heart failure
 - Not pregnant
 - Willing to take a urinary pregnancy test if there is a possibility of pregnancy
 - Able to freely provide informed consent

2. Cohort B: Participants in the LVAD (left ventricular assist device) body composition study (#12026) who consent to undergo skeletal muscle ultrasound the same day as an LVAD body composition study visit that already includes the DXA and handgrip strength procedures
 - Meet the eligibility criteria outlined in study #12026
3. Cohort C: Outpatients with heart failure, an LVAD or heart transplantation
 - 18+ years
 - Not pregnant
 - Willing to take a urinary pregnancy test if there is a possibility of pregnancy
4. Cohort D: Inpatients with heart failure, an LVAD or heart transplantation
 - 18+ years

Not pregnant

D.2 Exclusion Criteria

1. Describe the criteria that define who will be **excluded** in the study as a numbered list:
2. Exclusion criteria:
 1. Patients requiring temporary mechanical circulatory support
 2. Pregnant women, or women who report there is a possibility they could be pregnant and decline to complete a pregnancy test
3. Describe in detail how the eligibility criteria will be assessed and satisfied (e.g., medical record review, physical examination): **The eligibility criteria will be assessed by medical record review.**
4. State who will determine eligibility. Note that those who are designated to determine eligibility must have appropriate training, expertise, and oversight, for example a physician PI or Co-I on a biomedical study: **[name] will determine eligibility.**

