¹ **Undue influence**, often occurs through an offer of an excessive or inappropriate reward or other overture in order to obtain compliance. For example, an investigator might promise psychology students extra credit if they participate in the research. If that is the only way a student can earn extra credit, then the investigator is unduly influencing potential subjects. If, however, she offers comparable non-research alternatives for earning extra credit, the possibility of undue influence is minimized.

4. *To whom payment will be made (subject, parent [which one], legally authorized representative):*
5. *Payment schedule:*
 - a. *When payment will occur:*
 - b. *The payment schedule (amount at each time point), including details about the payment schedule and amount for subjects who withdraw or are withdrawn from the study:*

D.4.4 Reimbursement

Will subjects be reimbursed for their expenses, such as travel, parking, meals, or any other study related costs?

Yes No Yes No

E. Costs to Subjects

Does the research involve any costs to subjects?

Yes No Yes No

F. Study Design

F.1 Study Timelines

1. *Describe the duration of an individual subject's participation in the study:* one day, maximum 2 hours participation
2. *Describe the duration anticipated to enroll all study subjects at the Tufts study site:* 1 year
3. *Describe the estimated date for investigators to complete this study (complete primary analyses):* December 2019
4. *Describe the study procedures that will be accomplished at each study visit:* At each study visit, subjects in cohorts A, B, and C will undergo a whole-body DXA scan and all subjects will undergo an A-mode ultrasound at 7 anatomical landmarks on the dominant side, using the BodyMetrix Pro ultrasound (Intelametrix, Brentwood, CA).

F.2 Procedures

1. Is there a placebo control arm?
 Yes No Yes No
2. *Provide a description of all research procedures being performed as follows:*
 - a. *How individuals will be screened for eligibility. Specify screening that will take place prior to informed consent and screening that will take place after informed consent:*
 - Cohort A: Healthy volunteers (who may be employees)
 - Potential participants will be asked to confirm age >18 and no history of heart failure
 - Arrangements will be made for a urinary pregnancy test if there is a possibility of pregnancy

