- 1) Any experience when, based upon medical judgment, it may jeopardize the patient or subject and may require medical or surgical intervention to prevent one of the outcomes listed in this definition

H.2 Reporting Procedures

1. Describe the protocol-specific reporting procedures, including who will be responsible for each step (e.g., PI, Data Coordinating Center, Medical Monitor), which forms should be completed, timeframes for reporting, how reports will be distributed, and what follow-up is required: Any events, although not anticipated, will be reported to the IRB.
2. Include specific details of reporting procedures for:
 - a. Deaths, life-threatening events, pregnancies: Any events, although not anticipated, will be reported to the IRB.
 - b. Other SAEs: Any events, although not anticipated, will be reported to the IRB.
 - c. Other AEs: Any events, although not anticipated, will be reported to the IRB.
 - d. Other UPs: Any events, although not anticipated, will be reported to the IRB.

Ensure that the reporting procedures meet the reporting requirements of the FDA, NIH, OHRP, sponsor, study leadership and any other regulatory body that applies to the study, as applicable.

H.3 Reportable New Information

Check to confirm that reportable new information will be reported to the IRB per the Tufts Health Sciences IRB's [Reportable New Information policy](#). If your reporting plan to the IRB differs from the IRB's policies, please describe it in detail or specify where this information is in the protocol:

I. Statistical Considerations

I.1 Study Endpoints

1. Describe the primary and secondary study endpoints:

Primary DXA endpoint: fat free mass (FFM) measured by DXA

Primary ultrasound endpoint: FFM measured by BodyMetrix ultrasound

2. Describe any primary or secondary safety endpoints: N/A

I.2 Statistical Analysis

1. Describe the statistical analyses that will be performed for this study: Bland-Altman plot with bias and precision statistics to define the limits of agreement for FFM measured by DXA and ultrasound techniques.
2. Provide a power analysis: We previously showed good correlation between DXA and deuterium methods of FFM measurement in 8 patients with HF. Therefore we are aiming for a minimum enrollment of 60 subjects (10 per cohorts A-C, 30 per cohort D) and a maximum of 90 subjects total.

I.3 Number of Subjects

1. Specify the number of subjects to be enrolled in total across all sites: 90 or N/A this is not a multicenter study.

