2. Specify the number of subjects to be enrolled at the Tufts site. Subjects who sign an ICF are considered "enrolled". For studies that have a separate screening ICF, this number is the number of subjects who sign a screening ICF: 90
 - a. Provide the rationale for enrolling this number of subjects at the Tufts site: We plan to recruit a minimum of 60 subjects (10 per subgroups A-C, 30 per subgroup D) and a maximum of 90 subjects total.
 - b. Estimate the number of subjects expected to be enrolled at the Tufts site (i.e. sign the screening or study ICF) as well as the number needed to complete the study at the Tufts site: 90
 - c. If a large number of withdrawals and/or dropouts is expected, explain why: N/A

I.4 Data Management

1. Describe the data analysis plan, including descriptions of the data: Bland-Altman plot with bias and precision statistics to define the limits of agreement for FFM measured by DXA and ultrasound techniques. For skeletal muscle ultrasound to be considered a valuable technique for assessment of cachexia/sarcopenia, we would require the mean differences between the US and DXA measurement methods to be less than +/- 3, which is in line with our validation of DXA measurement of fat-free mass using the deuterium reference technique.
2. Provide a power analysis: See above
3. Describe the steps that will be taken to secure the data (e.g., training, authorization of access, password protection, encryption, physical controls, certificates of confidentiality, and separation of identifiers and data) during storage, use, and transmission: The data will be stored only on Tufts MC networked folders with password protection and accessed within accessed-controlled academic hospital areas.
4. Describe any procedures that will be used for quality control of collected data: Review of data by PI
5. Describe how data and specimens will be handled study-wide as follows:
 - a. What information will be included in that data or associated with the specimens: Subject number, sex, age, weight, body mass index, heart failure status.
 - b. Where and how data or specimens will be stored: N/A
 - c. How long the data or specimens will be stored: N/A
 - d. Specify who will have access to the data or specimens: Research team members only
 - e. Specify who is responsible for receipt or transmission of the data or specimens: N/A
 - f. Specify how data and specimens will be transported: N/A

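### The only pass rule is a pooled mean ultrasound–DXA difference within +/- 3, so ultrasound could pass while outside that limit in low-FFM patients; no check of bias by FFM level or by healthy versus patient status is specified.

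*Combined protocol and SAP*

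**What the plan says.** Section I.2, item 1 gives the whole analysis: "Bland-Altman plot with bias and precision statistics to define the limits of agreement for FFM measured by DXA and ultrasound techniques". Section I.4, item 1 repeats it and adds the only criterion for calling ultrasound valuable in assessing cachexia or sarcopenia: "we would require the mean differences between the US and DXA measurement methods to be less than +/- 3". No unit is attached to the 3, and no requirement is set on the width of the limits of agreement.

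The power-analysis item in I.2 gives a minimum of 60 subjects ("10 per cohorts A-C, 30 per cohort D") and a maximum of 90. Under F.1, item 4, "subjects in cohorts A, B, and C will undergo a whole-body DXA scan and all subjects will undergo an A-mode ultrasound". Cohort A is healthy volunteers, B is LVAD-study participants, and C is outpatients with heart failure, an LVAD or a transplant (D.1). The inpatients of cohort D are not listed for DXA.

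On intended use, B.1, item 4 says: "Measuring muscle mass will allow us to identify patients with HF who are experiencing muscle wasting". The secondary aim in section C is to classify patients as cachectic or sarcopenic. B.1, item 2 acknowledges that the team has no muscle ultrasound data in this population.

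The document names no regression of the difference on FFM, transformation, estimate by cohort or by healthy versus patient status, or estimate at low FFM.

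**The concern.** A single mean difference describes agreement well only if the bias is about the same at every FFM level and in every kind of subject. The paired sample mixes healthy volunteers with patients, and the protocol expects wasting among the sickest of them: "as many as half of end-stage systolic HF patients have significant sarcopenia at the time of LVAD implantation". If ultrasound reads too high in subjects with little lean tissue and too low in those with much, the two errors offset each other in the one quantity that has a pass rule.

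The conclusion drawn from that rule is about finding wasted patients, so accuracy at low FFM matters most. Followed exactly, the plan could declare the method valuable for that purpose while its bias there exceeds the sponsor's own limit.

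**Working it through.** **Inputs from the documents.** Limit +/- 3. Cohorts: 3 x 10 + 30 = 60, which reproduces the stated minimum. Pairs: 3 x 10 = 30 at the minimum, and 90 - 30 = 60 at the maximum if cohort D stays at 30. Healthy share at the minimum: 10/30. No alpha, power, SD of FFM or SD of differences is given, so there is no planned precision to reproduce.

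**Algebra, with no assumed values.** Write d = ultrasound minus DXA = a + b(FFM - mean FFM) + e. The expected mean of d is a, whatever b is. The pass rule therefore carries no information about b. The spread does respond: SD(d)² = b² x SD(FFM)² + SD(e)².

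**Illustration.** Assumed, not in the documents: a = 0, mean FFM 55, SD(FFM) 10, SD(e) 4, slope on DXA FFM, limit in the units of FFM.

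- Bias at FFM 40: 0.3 x (55 - 40) = 4.5 at slope -0.3, which is 1.5 times the limit; 0.2 x 15 = 3.0 at slope -0.2.
- SD(d) at slope -0.3: sqrt(4² + 3²) = 5.0. Limits of agreement are about +/- 1.96 x 5.0 = +/- 9.8, against +/- 7.8 with no slope.
- SE of the mean with 30 pairs: 5.0/sqrt(30) = 0.913. Since 3/0.913 = 3.29, the rule passes about 99.9% of the time. Simulation (20,000 runs) agrees, and gives 100% at 60 pairs.

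**Range.** Simulations varied SD(FFM) over 8, 10 and 12 with SD(e) 3, SD(e) over 2, 4 and 5 with SD(FFM) 10, and the slope over -0.2, -0.3 and -0.4. The bias 1.5 SD below the mean runs from 2.4 to 7.2, and the rule passes in 99% to 100% of runs throughout.

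**By cohort, 10 pairs each.** True biases of -8, +4, +4 pool to (-80 + 40 + 40)/30 = 0. Biases of -5, +4, +4 pool to (-50 + 40 + 40)/30 = +1.0. Both pass with every cohort outside +/- 3.

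**What a slope analysis would deliver at 30 pairs (same assumptions).** The x-axis matters.

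- On DXA FFM at slope -0.3: SE = 4/(10 x sqrt(29)) = 0.074, t about 4.0, simulated power about 96%.
- On the average of the methods: the average contains half the ultrasound error, so the expected slope is (-0.3 x 0.85 x 100 + 16/2)/(0.85² x 100 + 16/4) = -17.5/76.25 = -0.23. Mean t is about 2.4 in size and power about 61%. At slope -0.2 power is about 26%.
- On the average with no true slope and all error in ultrasound: expected slope 8/104 = +0.08, with 18% false rejection at 30 pairs and 33% at 60.
- Precision of the predicted bias at FFM 40, regressing on DXA: SE = 4 x sqrt(1/30 + 15²/(29 x 100)) = 1.33, so the 95% CI is about +/- 2.05 x 1.33 = +/- 2.7.
- Precision of the bias in one cohort of 10, with SD of differences 2 to 5: 95% CI +/- 1.4 to +/- 3.6.

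**The case against.** The strongest reply is that nothing is concealed. A Bland-Altman plot displays the difference against level, and a slope widens the reported limits, so a careful reader would notice. That stands as far as display goes: a reader might infer that the plan would hide the failure altogether, and it would not. But no action is tied to the plot or the limits, so the pass rule is unaffected.

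A reader might also infer that the plan assumes one constant bias. It does not say so. It is silent on pooling, and its wording about mean differences is loose. A single pooled mean is the plain reading because no breakdown is named.

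The contrast between healthy and wasted subjects is partly assumed. No FFM distribution is given. Cohort C includes transplant recipients and outpatients with any heart failure, and B.1 reports that muscle mass improves after LVAD implantation. Low absolute FFM also reflects sex and body size. This stands, and is why bias by healthy versus patient status is needed alongside a slope on FFM.

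It would be tempting to say that 30 pairs would reveal such a slope easily. That holds for regression on DXA FFM under the assumed values, but not for regression on the average.

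Finally, the study is described as generating preliminary data, and the check could be added afterwards. Both are true, but the protocol states its pass rule in advance, and a check chosen after seeing the data carries less weight.

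**Conclusion.** The concern holds for the acceptance rule. That the mean difference ignores any FFM-dependent error is algebra and rests on no assumption. The illustrated size, a bias of +4.5 at FFM 40 with about a 99.9% chance of passing at 30 pairs (+3.0 at slope -0.2), rests wholly on assumed values and on reading the unitless limit in FFM units.

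The documents do not support the stronger reading that ultrasound does misjudge wasted patients: they contain nothing on the existence, size or direction of such error. The amendment should be made before analysis. It is an inexpensive improvement to a preliminary validation study, not a flaw that invalidates it.

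**What to change.** Amend I.2 and I.4 as follows.

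1. Pre-specify a regression of the ultrasound–DXA difference on FFM level, and state and justify the x-axis: DXA as the reference, or the average of the methods with its distortion under unequal error acknowledged. Report the slope, and the predicted bias at low FFM (for example the lower quartile among patients), with 95% CIs. Do not rely on a p-value.
2. Report bias and limits of agreement separately for healthy volunteers and for patients.
3. Apply the existing +/- 3 limit, with its unit stated, to the bias in patients and to the predicted low-FFM bias as well as to the pooled mean. Give regression-based limits if the slope is not near zero.

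The cost is a few sentences and a little extra analysis. FFM by both methods and heart failure status are already collected. The downside is imprecision: with 30 to 60 pairs, low-FFM and subgroup estimates will have wide intervals, which should be reported beside each comparison with the limit.

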	K.7 Sharing Results with Subjects	18
L.	References	18

Study Schema

Include a diagram that provides a quick “snapshot” of the study. For examples of study schemas, refer to the [FDA and NIH’s Study Schema Examples](#) document available on the IRB website:

A. Introduction

B.1 Background and Rationale

1. *Describe the relevant prior experience and gaps in current knowledge:* We have been using the dual-energy X-ray absorptiometry (DXA) scan to measure muscle mass of patients with heart failure (HF). As the participants in these HF body composition studies are deconditioned, walking over to the DXA scan facility at [name] can limit its use. Using a mobile hand-held ultrasound apparatus would provide a more patient-friendly method of measuring muscle mass, and we would like to generate data on its validity. We plan to compare muscle mass measurements from DXA scanning to muscle ultrasound to validate the ultrasound method.
2. *Describe any relevant preliminary data:* We have substantial experience using DXA to measure body composition in patients with HF, but no data on skeletal muscle US in this population, or the comparison between DXA and US - hence the need to for this study to generate preliminary data.

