 5. Are there any risks to study investigators or staff performing the study procedures due to research with high risk populations (e.g. prisoners, intravenous drug users, patients with major psychiatric issues, etc.):?

Yes No Yes No

B.3 Potential Benefits to Subjects

1. Describe the potential benefits that individual subjects may experience from taking part in the research. Include the probability, magnitude, and duration of the potential benefits: There are no direct benefits to individual subjects; however, subjects will obtain information regarding their body composition, which they may find interesting.

Note: Payments and incentives are not considered benefits in the IRB's risk-benefit assessment; payment and incentives should be addressed in the payment section.

2. Check if there is no direct benefit.
3. Describe any benefit to the population from which the subject is drawn: This study will determine if the use of the hand-held ultrasound is comparable to that of the DXA scan. Current AHA LVAD Body Composition subjects must walk or be wheel-chaired to the HNRCA at [name] to undergo the DXA scan. If this study proves the ultrasound applicable for muscle mass measurements, it will provide a less strenuous method of measuring muscle mass for the Body Composition Study. or N/A
4. Describe any benefit to science, society, and humanity in general: This study will validate the applicability of ultrasound muscle thickness measurements as a method to evaluate muscle mass. This will provide the cardiology community with a quicker, non-intrusive, patient-friendly method of measuring muscle mass in this patient population. or N/A

B.4 Alternatives

1. Describe alternatives to participating in this research study (e.g. to decide not participate in the study, alternative treatments, no treatment (palliative care), etc.): Subjects can decide not to participate in the study.
2. Describe the standard clinical care that may be an alternative: or N/A
3. Describe how the subject can receive the research procedures/drug/device used in this study in a non-research setting: or N/A

C. Objectives

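### The only numeric acceptance criterion for ultrasound is a mean difference from DXA below +/- 3 (no unit); it screens out bias but not individual error, because the planned limits of agreement have no acceptable bound

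*Combined protocol and SAP*

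**What the plan says.** The analysis, given in I.2 item 1 and repeated in I.4 item 1, is a "Bland-Altman plot with bias and precision statistics to define the limits of agreement for FFM measured by DXA and ultrasound techniques". I.4 item 1 then adds the one numeric condition for regarding ultrasound as valuable in cachexia or sarcopenia assessment: "we would require the mean differences between the US and DXA measurement methods to be less than +/- 3". The margin carries no unit. It is said to be in line with the team's DXA-deuterium validation, but no bias, SD or LoA from that work is given. No section says how wide the LoA may be.

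The documents describe two kinds of use.

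- **Patient level.** B.1 item 3 seeks the "utility of skeletal muscle ultrasound (US) as a novel method for sarcopenia diagnosis in patients with heart failure", and B.1 item 4 says "The use of muscle ultrasound as a portable and non-ionizing screening method furthers our efforts".
- **Research.** The hypothesis in B.1 item 3 is that DXA appendicular lean mass (ALM) "will show adequate agreement with skeletal muscle US in systolic HF patients for deployment in our future HF body composition studies", with no number attached. B.3 item 3 says that, if ultrasound proves applicable, "it will provide a less strenuous method of measuring muscle mass for the Body Composition Study".

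B.1 item 2 describes the study as preliminary: there are no earlier ultrasound data in this population, "hence the need to for this study to generate preliminary data".

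**The concern.** A mean difference measures average bias. Positive and negative errors cancel in it, so it can be near zero while single patients are badly misjudged. That may be acceptable for comparing group averages in research. It is not enough for diagnosing or screening a patient, which depends on the spread of individual differences.

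The LoA describe that spread and will be reported, so large errors would be visible. With no bound set beforehand, however, whether they are tolerable would be decided after the data are seen, by a team with no earlier ultrasound-DXA data in this population to guide the judgement.

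**Working it through.** **Inputs from the documents**
- Margin: 3, unit not stated (I.4 item 1).
- Enrolment: minimum 60, that is 3 x 10 + 30 = 60; maximum 90 (I.2 item 2, I.3 item 2a). The sum checks. No alpha, power, SD or expected bias is given, so there is no sample-size calculation to reproduce.
- Pairs: F.1 item 4 says "subjects in cohorts A, B, and C will undergo a whole-body DXA scan". Cohort D is not included, so minimum enrolment gives 3 x 10 = 30 pairs.

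**Assumptions**
- Differences are normal, with one pair per subject.
- SD of differences is 2, 3, 5 or 8, in the margin's own unit.
- For a larger sample, 60 pairs: 90 enrol and cohort D stays at 30.

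**Step 1. Does the criterion catch bias?** For true bias b, the chance of meeting it is Phi((3 - b)/SE) - Phi((-3 - b)/SE), with SE = SD/sqrt(n). With SD 5 and n = 30, SE = 5/5.477 = 0.913.
- b = 0: 3/0.913 = 3.29, so 99.9%.
- b = 2: (3 - 2)/0.913 = 1.10, so 86%.
- b = 4: (3 - 4)/0.913 = -1.10, so 14%.

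It does.

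**Step 2. Does it limit individual error?** At zero bias the LoA are +/- 1.96 x SD, and the share of individuals who differ by more than 3 is 2 x (1 - Phi(3/SD)).

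| SD (assumed) | LoA | Individuals differing by more than 3 | Criterion met, 30 pairs | Criterion met, 60 pairs |
|---|---|---|---|---|
| 2 | +/- 3.9 | 13% | about 100% | about 100% |
| 3 | +/- 5.9 | 32% | about 100% | about 100% |
| 5 | +/- 9.8 | 55% | 99.9% | about 100% |
| 8 | +/- 15.7 | 71% | 96% | 99.6% |

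It does not. At zero bias, more pairs make the criterion easier to meet but leave the true LoA unchanged.

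**Step 3. What would a bound on the LoA add?** Suppose both estimated LoA must also lie within +/- M, that is |mean| + 1.96 x S < M, where S is the sample SD. Simulation at zero bias and 30 pairs gives the table below. The values of M are illustrative, not proposals.

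| M | SD 2 | SD 3 | SD 5 | SD 8 |
|---|---|---|---|---|
| 6 | 99.9% | 39% | 0% | 0% |
| 8 | about 100% | 98% | 3% | 0% |
| 10 | about 100% | about 100% | 38% | 0% |

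The bound separates SDs well away from M/1.96, but not those near it. At SD 3 the true LoA (+/- 5.88) lie inside M = 6, and at SD 5 the true LoA (+/- 9.8) lie inside M = 10, yet the rule is met only 38-39% of the time. With 60 pairs it is met about 40% of the time in both cases.

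**Step 4. How precise are the LoA?** The 95% CI half-width of each limit is t x SD x sqrt(1/n + 1.96^2/(2(n - 1))).
- 30 pairs: 2.045 x SD x sqrt(0.0333 + 0.0662) = 0.65 SD, which is about +/- 3.2 at SD 5.
- 60 pairs: 2.001 x SD x sqrt(0.0167 + 0.0326) = 0.44 SD, which is about +/- 2.2 at SD 5.

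**The case against.** **The criterion is necessary, not sufficient.** The wording is a requirement. A reader might infer that meeting it would by itself validate ultrasound for diagnosis; the text does not say so, and the LoA are a planned output. This stands. What remains is that no other requirement is written.

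**The margin may have been meant for the LoA.** It follows directly on a sentence about LoA, and its basis cannot be seen. The literal reading, a mean difference, is the better one, but the point needs confirming because the two readings differ greatly. At SD 2, zero bias and 30 pairs, the mean criterion is met about 100% of the time, whereas both estimated LoA fall within +/- 3 only about 1% of the time.

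**The use is mainly research, and the study is preliminary.** The hypothesis speaks of future studies, and the secondary aim of categorising patients (section C) does not name ultrasound. This limits the severity. It does not remove the point, because the criterion itself concerns cachexia and sarcopenia assessment, and B.1 names diagnosis and screening.

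**The SDs are assumed.** True. A reader might infer that individual errors will be large. The documents give no SD of ultrasound-DXA differences, so the figures show only what the criterion would allow.

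**Conclusion.** The point holds, as something that should be fixed. The one numeric criterion tests average bias and does that usefully; a reader who concluded that it tests nothing would be wrong. It leaves individual error unbounded. With 30 pairs and zero bias it would be met 99.9% of the time with LoA of +/- 9.8 and 96% with LoA of +/- 15.7, and more often with 60 pairs.

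These figures rest on assumed SDs in an unstated unit and on normal differences. If the SD is near 2, the gap is small.

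A reader might also infer that a bound on the fat-free mass (FFM) LoA would settle diagnostic use. It would not: the hypothesis concerns ALM, the endpoints in I.1 are FFM, and the documents give no sarcopenia cut-off.

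**What to change.** Amend I.4 item 1 before analysis:

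- **(a)** State the unit of the +/- 3 margin, and confirm that it applies to the mean difference and not to the LoA. Only the investigators can supply this.
- **(b)** Keep the mean-difference margin as the criterion for group-level research use, and report the 95% CI of the mean difference.
- **(c)** Pre-state a maximum acceptable individual FFM difference M, in the same unit and justified by the investigators. Claim individual-level FFM agreement only if both estimated 95% LoA lie within +/- M, and report the 95% CI of each limit.
- **(d)** If the mean criterion is met but (c) is not, limit the conclusion to group-level agreement.

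State also that meeting (c) is necessary but not sufficient for a diagnostic or classification claim.

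**Cost.** This is a change of wording with no extra patients, and the group-level conclusion is as easy to reach as now. The individual-level conclusion becomes harder to reach. A method whose true LoA lie just inside M would fail about 60% of the time with either 30 or 60 pairs, and each limit will be imprecise. The investigators should weigh this when they choose M.
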